#### **7.1.2 Two-separated procedures**

The risks of the operations are according to each operation individually. Focal therapy for prostate cancer (HIFU and Cryoablation) is routinely performed by USC urologists. In fact, we have one of the largest experiences with ablation therapy for PCa in the US [42,47]. These procedures are safe with low risk of perioperative complications and lower risks of severe adverse events. In our initial series of 100 consecutive men who underwent HIFU focal therapy for PCa, approximately 13% of the patient experienced adverse events being the most common urinary retention, requiring prolonged catheterization, and urinary infection, requiring antibiotics [39]. No patient underwent additional intervention due to complications/adverse events. Additionally, there were no anesthesia-related complications. It is important to note that these patients were treated with a curative intent with large areas of ablation often extending towards to the urethra. Recent trials investigating TMA also demonstrated the feasibility and safety [26-28]. For the current PRAMA study, the TMA approach will be more conservative because the intent isn't curative, therefore the urethra and surrounding organs will be preserved. As such, we expect lower chances of side effects. The anesthesia risks related to RALP is similar to the approximately 600

---

RALPs annually performed by USC urology. The anesthesia risk shouldn't be affected by the TMA prior to RALP.

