## 7.3 Definition

### 7.3.1 Definition of Adverse Event

An adverse event (AE) is any untoward medical occurrence in a patient receiving study treatment and which does not necessarily have a causal relationship with this treatment. Based on pilot data, there are no adverse events associated with performing TMA in patients who are candidates for RP. The AEs of interest for this study include:

Acute urinary retention: any episode of urinary retention following surgery, needed catheterization.

Hematuria: Any gross blood/clot in the urine, needed bladder irrigation.

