#### Clavien Dindo Classification (CDC)

Grade I	Any deviation from the normal postoperative course without the need for pharmacological treatment or surgical, endoscopic and radiological interventions Allowed therapeutic regimens are: drugs as antiemetics, antipyretics, analgetics, diuretics and electrolytes and physiotherapy. This grade also includes wound infections opened at the bedside.
Grade II	Requiring pharmacological treatment with drugs other than such allowed for grade I

---

	complications. Blood transfusions and total parenteral nutrition are also included.
Grade III	Requiring surgical, endoscopic or radiological intervention
IIIa	Intervention not under general anesthesia
IIIb	Intervention under general anesthesia
Grade IV	Life-threatening complication (including CNS complications)* requiring IC/ICU-management
IVa	Single organ dysfunction (including dialysis)
IVb	Multi organ dysfunction
Grade V	Death of a patient

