## **7.7 Monitoring Rules for Safety**

All other adverse events- such as those that are expected or are unlikely or definitely not related to the study participation- are to be reported as part of regular data submission.

---

We will pause study enrollment after 10 patients if 2 or more patients do not progress to RP and perform a thorough assessment as to ongoing safety of the study.

If a severe adverse event related to TMA occurs during TMA procedure or by follow-up phase (Day 10 ± 5) for immediate resection phase or by follow-up phase 3 (Day 40 ± 5) for delayed resection phase, we assess, discuss, and tabulate the severe adverse event.

To ensure safety, the next patient's TMA will be scheduled at least after follow-up phase of the previous patient for immediate resection phase. For delayed resection phase, the next patients for the different TMA template will be scheduled at least after follow-up phase 3 of the previous patients.

In addition, for the delayed resection phase, in the case that two in two patient who underwent the same TMA template experienced severe adverse events related to TMA, we stop to proceed the next TMA template.

We set 30% as clinically acceptable severe adverse events (defined as CDC ≥3) rate (i.e. less than 4 in 10 delayed resection cases).

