## 10.7 Data Analyses Plans

All patients who sign the consent form will be registered and entered the database. For each patient, we will list whether he received the assigned protocol (and if not, the reasons), the outcome of the procedures, compliance with the protocol (and reasons for failure to comply), adverse events with any of the procedures, MRI results, and targeted biopsy results.

- The data from the immediate resection phase and delayed resection phase will be separately evaluated. The observed ablated area in immediate resected prostatectomy specimen based on TTC staining will be compared with the predicted ablation area according to the template. The tissue viability will be evaluated by HE staining on delayed resection prostatectomy specimen.
- The comparison of the difference between the treatment effect dimensions measured histologically on the prostatectomy specimen resected after TMA and the predictive ablation charts provided by the manufacturer will be performed. For this analysis, the data from immediate resection phase and delayed resection phase are separately evaluated.
- The comparison between the treatment effect dimensions measured histologically on the prostatectomy specimen resected one month after TMA, compared to post TMA dimensions measured on the pre-RP mpMRI.
- To evaluate the intra/post-operative safety of TMA, we defined 30% as clinically acceptable severe adverse events (defined as CDC  $\geq 3$ ) rate. If the severe adverse events occur less than 30% (equivalent to less than 4 cases in 10 cases) for the delayed ablation phase, the feasibility of TMA is proved.

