### Delayed resection phase

If a severe adverse event related to TMA occurs during TMA procedure or by follow-up phase 3 (Day  $40 \pm 5$ ), we assess, discuss, and tabulate the severe adverse event. In the case that two in two patient who underwent the same TMA template experienced severe adverse events related to TMA, we stop to proceed the next TMA template. For this evaluation, TMA-related adverse events include rectal injury, urethral injury, acute urinary retention, and uncontrollable hematuria.

Adverse events are also recorded in accordance with Common Terminology Criteria for Adverse Events (CTCAE) v5.0.

- TMA procedure duration: probe-in / probe-out time, ablation time will be recorded.
- The ablation location in the prostate as seen in the KOELIS 3D map and the ablation location observed histologically on the prostatectomy specimen will be recorded.

---

- The change in functional outcomes between baseline and each follow-up visit, using IPSS, IIEF-5, EPIC-26 and uroflowmetry is recorded. For delayed resection phase, functional outcomes between baseline and follow-up phase 2 will be estimated as average change.
- The post-TMA MRI and prostate biopsy performed just prior to the delayed radical prostatectomy will be reported.

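### Feasibility is declared proved from the CDC grade 3 or higher count alone, and the plan does not say how its own adverse events of interest are graded

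*Combined protocol and SAP*

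**What the plan says.** Section 10.7 sets the safety criterion: "To evaluate the intra/post-operative safety of TMA, we defined 30% as clinically acceptable severe adverse events (defined as CDC" grade 3 or higher). The decision follows: "If the severe adverse events occur less than 30% (equivalent to less than 4 cases in 10 cases) for the delayed ablation phase", feasibility is taken as proved. Section 7.7 repeats the limit: "We set 30% as clinically acceptable severe adverse events (defined as CDC ≥3) rate (i.e. less than 4 in 10 delayed resection cases"). Section 7.3.2 makes CDC the scale on which safety is judged; CTCAE v5.0 is recorded alongside it.

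Section 7.3.1 names two adverse events of interest and gives neither a grade:

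- "Acute urinary retention: any episode of urinary retention following surgery, needed catheterization"
- "Hematuria: Any gross blood/clot in the urine, needed bladder irrigation"

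The CDC table in section 7.3.2 defines grade III as "Requiring surgical, endoscopic or radiological intervention", with IIIa for interventions done without general anesthesia and IIIb for those done with it. The table does not mention catheters or irrigation.

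Under the delayed resection heading of section 10.7, the evaluation of severe events, including the rule that halts progression when both men on a template have one, states that "TMA-related adverse events include rectal injury, urethral injury, acute urinary retention, and uncontrollable hematuria".

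**The concern.** The verdict has one input, the number of the 10 delayed-phase men with a CDC grade 3 or higher event. The harms that the plan singles out are defined by measures which the printed grade III does not clearly include. If they are graded below III, a TMA that leaves no man with urinary morbidity and one that puts every man into catheter-treated retention get the same verdict. If graders treat a catheter or irrigation as a IIIa intervention, the second TMA fails outright. A convention written nowhere would then decide the trial's only formal conclusion on safety and feasibility. Section 10.2 gives short-term safety after TMA as one reason for having the delayed phase.

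**Working it through.** **1. The plan's own boundary.** Section 10.7 equates a rate below 30% with fewer than 4 of 10. But 3/10 = 30%, which is not below 30%. Strictly, below 30% allows 0 to 2 events, while fewer than 4 allows 0 to 3. The two agree only if the limit is read as at most 30%. I use fewer than 4 as the main reading, because it stands in both 7.7 and 10.7, and show the stricter limit beside it.

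**2. Definitions side by side.**

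| Event (7.3.1) | Minimum needed to qualify | In printed CDC grade III? |
|---|---|---|
| Acute urinary retention | Catheterization | Not named |
| Hematuria | Bladder irrigation | Not named |

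Section 7.1.2 points to a grade below III. It describes a HIFU series of 100 men in which retention with prolonged catheterization was among the most common events, and then says: "No patient underwent additional intervention due to complications/adverse events". So in that passage a catheter is not called an intervention. This is usage in prose and assigns no grade.

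**3. How the grading moves the verdict.** Let q be the share of delayed-phase men with a section 7.3.1 event, and f the chance that such an event is graded CDC 3 or higher. The documents do not give f, so I assume values from 0 to 1. Assume also that no other severe events occur, that men are independent with the same risk, and that all 10 are treated. The severe count X is then binomial with n = 10 and p = q × f, and

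P(pass) = Σ C(10,k) p^k (1−p)^(10−k), summed over k = 0 to 3 (or 0 to 2 for the strict limit).

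For q = 1 and f = 0.5: (1 + 10 + 45 + 120)/1024 = 176/1024 = 0.172.
For q = 1 and f = 0.25: 0.0563 + 0.1877 + 0.2816 + 0.2503 = 0.776.

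| q | f | p | P(pass), fewer than 4 | P(pass), below 30% |
|---|---|---|---|---|
| 1.0 | 0 | 0 | 1.000 | 1.000 |
| 1.0 | 0.25 | 0.25 | 0.776 | 0.526 |
| 1.0 | 0.5 | 0.5 | 0.172 | 0.055 |
| 1.0 | 1 | 1 | 0 | 0 |
| 0.8 | 0.25 | 0.2 | 0.879 | 0.678 |
| 0.8 | 0.5 | 0.4 | 0.382 | 0.167 |
| 0.5 | 0.25 | 0.125 | 0.973 | 0.880 |
| 0.5 | 0.5 | 0.25 | 0.776 | 0.526 |

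At f = 0 the pass probability is 1 for every q. The two-in-two rule also counts severe events, so it would not fire either. In the middle rows that rule could end the phase before 10 men are treated, which the table ignores.

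**4. The extreme case as it would be reported.** With all 10 men affected and none graded 3 or higher, the any-grade result is 10/10, with exact 95% lower limit 0.025^(1/10) = 69%. The severe count is 0/10, with upper limit 1 − 0.025^(1/10) = 31%. The verdict would be that feasibility is proved.

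**The case against.** A rule on severe events that does not respond to non-severe events is doing what it was built to do, and choosing grade 3 as the cut for a 10-man phase is a legitimate design decision. The f = 0 case largely restates that choice. The harms are not lost either. Section 2.5 makes the number and severity of device- and procedure-related events a secondary endpoint with no grade cut. Section 10.7 lists each patient's adverse events, and section 10.8 names retention and hematuria for monitoring. Section 5.4.4 measures IPSS, EPIC-26 and uroflowmetry before RP. Morbidity in all 10 men would be visible in the report. All of this stands. It means that the data will exist; it does not bring them into the sentence that declares feasibility.

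Three stronger readings are tempting, and the documents do not support them:

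- A reader might infer that retention and hematuria are certainly below grade III. No section grades them, a grader could argue for IIIa, and cases needing endoscopy or surgery would count.
- A reader might take the delayed-phase event list in 10.7 as a flat contradiction of the CDC cut. It can be read as event types that count only once they reach grade 3. Its hematuria entry is also limited to uncontrollable cases, which is narrower than the 7.3.1 definition.
- A reader might turn the HIFU series in 7.1.2 into a grade III rate of 0/100, or use its figure of about 13% as a benchmark. The statement about additional intervention is not a CDC tabulation. The 13% covers any adverse event, infection included, after curative-intent HIFU with large ablation areas. Neither is like-for-like with TMA here.

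**Conclusion.** The concern holds in a conditional form. The conclusion that feasibility is proved rests only on the CDC grade 3 or higher count in 10 men, and the plan leaves open whether its own adverse events of interest can enter that count. On the plain wording of the CDC table, supported by the usage in 7.1.2, events at their minimum definition would not enter it at any frequency. That is a well-supported inference, not a stated rule. The size of the problem is the spread in P(pass) when every man is affected: from 1.000 to 0 under either limit, depending only on grading. The intermediate values depend on the assumed f and on independence between men, which the escalating templates make approximate. The point concerns what the verdict may claim and how events are classified. It does not show that the grade 3 cut is wrong or that adverse events go unreported.

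**What to change.** 1. In section 10.7, replace the statement that feasibility is proved with one limited to what was measured: the CDC grade 3 or higher rate in the delayed phase was, or was not, within the stated limit.
2. Beside it, report the number of delayed-phase men with a section 7.3.1 event of any grade between TMA and RP, as n/10 with an exact 95% confidence interval and without the HIFU figure as comparator. State how the planned catheter period is handled: section 5.3.7 allows discharge with a catheter and the study calendar removes it at Day 10, so retention defined by needing a catheter is hard to identify before then. This is a descriptive result. With no limit attached, it should not be presented as a second decision rule.
3. Reconcile 7.3.1, the CDC table in 7.3.2 and both parts of 10.7. State before data are seen how events treated by catheterization or irrigation are graded. If it is what is meant, state also that the event types in the delayed-phase list enter the severe count only at CDC grade 3 or higher. Settle the below 30% versus fewer than 4 wording in the same edit.

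The cost is protocol wording and one table row. The study calendar already assesses adverse events at Day 10, at follow-up phase 2 and on the RP date, so no visits or patients are added. The safety conclusion will read less favourably, and the interval will be wide: even 0/10 gives 0 to 31%.

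### Ten delayed-resection patients cannot prove a severe-event rate below 30%; the pass rule is also undefined at 3 of 10 and can count prostatectomy complications

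*Combined protocol and SAP*

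**What the plan says.** The criterion appears twice. Section 7.7 (Monitoring Rules for Safety) has "We set 30% as clinically acceptable severe adverse events (defined as CDC ≥3) rate (i.e. less than 4 in 10 delayed resection cases". Section 10.7 (Data Analyses Plans) repeats it as "To evaluate the intra/post-operative safety of TMA, we defined 30% as clinically acceptable severe adverse events" and adds the decision: if severe events occur in "less than 30% (equivalent to less than 4 cases in 10 cases) for the delayed ablation phase, the feasibility of TMA is proved".

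Three other provisions bear on it.

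- **Sample size.** Section 10.6 bases the 15 patients on cost and practicality. It gives no error rate, power or target precision for the safety criterion.
- **Window and attribution.** Under the delayed-resection subheading of 10.7, and in 7.7, severe events related to TMA are assessed up to follow-up phase 3 (Day 40 ± 5). The study calendar puts RP at Day 30 (± 5). Those sentences refer to TMA-related events; the 30% rule carries no such restriction and names no window of its own.
- **Template rule.** If both patients on one template have TMA-related severe events, the study does not go on to the next template.

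**The concern.** The trial has no control arm, so this rule is what turns the delayed-phase safety data into a conclusion. Three things go wrong.

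1. The rule compares a point estimate from 10 patients with the limit and calls the outcome proof. Sampling error is ignored, and at n = 10 it is very large.
2. The limit is written in two ways that give different answers at one attainable count, 3 of 10. An outcome whose result can be chosen after the data are seen is not pre-specified.
3. The count can mix two operations. Nothing in the rule separates a severe event caused by TMA from one caused by the RP about a month later. The mixing could make TMA look worse than it is, and it leaves the verdict not specific to TMA either way.

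At stake is whether a report can say that TMA was shown to be acceptably safe, when the data would be compatible with severe-event rates well above the plan's own ceiling.

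**Working it through.** **Inputs.** n = 10 delayed-resection patients; limit 30%; pass count fewer than 4 (7.7 and 10.7). Confidence limits are exact (Clopper-Pearson). Pass probabilities are binomial, assuming independent patients with a common true rate p.

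**1. The plan's own figure.** Section 10.7 equates a rate under 30% with fewer than 4 of 10. Since 3/10 = 30%, which is not under 30%, a rate under 30% means at most 2 events. Fewer than 4 means at most 3, which fits only if a rate equal to 30% is allowed. The stated equivalence is not reproduced. Section 7.7 gives 30% as the acceptable rate with fewer than 4 of 10, which fits the second reading only.

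**2. What a passing count shows.** For x = 0 the two-sided 95% upper limit is 1 − 0.025^(1/10) = 0.3085.

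| Events | Two-sided 95% interval | One-sided 95% upper limit | Passes under 30%? | Passes fewer than 4? |
|---|---|---|---|---|
| 0/10 | 0 to 0.3085 | 0.259 | yes | yes |
| 1/10 | 0.0025 to 0.4450 | 0.394 | yes | yes |
| 2/10 | 0.0252 to 0.5561 | 0.507 | yes | yes |
| 3/10 | 0.0667 to 0.6525 | 0.607 | no | yes |

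No passing count excludes 30% at the two-sided 95% level. At the one-sided 95% level only 0/10 does.

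**3. How often an unacceptable rate passes.** At p = 0.30 the probabilities of 0, 1, 2 and 3 events are 0.0282, 0.1211, 0.2335 and 0.2668.

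- At most 3: 0.0282 + 0.1211 + 0.2335 + 0.2668 = 0.650.
- At most 2: 0.0282 + 0.1211 + 0.2335 = 0.383.

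| True rate | P(at most 3) | P(at most 2) |
|---|---|---|
| 20% | 0.879 | 0.678 |
| 30% | 0.650 | 0.383 |
| 40% | 0.382 | 0.167 |
| 50% | 0.172 | 0.055 |

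Read as a test of the hypothesis that the rate is 30% or more, the rule has a type I error of 0.65 or 0.38.

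**4. Adding the template rule.** Assume every severe event is TMA-related, and require that none of the first four pairs has two events out of two. Each pair at p = 0.30 has 0, 1 or 2 events with probability 0.49, 0.42 or 0.09. Four such pairs without a double give 0, 1, 2 or 3 events with probabilities 0.0576, 0.1977, 0.2541 and 0.1452. Adding the fifth pair:

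- At most 3: 0.49 × 0.6546 + 0.42 × 0.5094 + 0.09 × 0.2553 = 0.558.
- At most 2: 0.49 × 0.5094 + 0.42 × 0.2553 + 0.09 × 0.0576 = 0.362.

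The template rule lowers the pass probability only modestly (0.65 to 0.56, 0.38 to 0.36).

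**5. Which events count.** Set side by side, the template rule and the tabulation rule are limited to events related to TMA, and the 30% rule is not. The delayed-phase tabulation runs to Day 40 ± 5, about 10 days after RP. If the 30% rule uses the same window, severe complications of RP fall inside it. Even under a restriction to TMA-related events, two of the four event types that 10.7 lists for this phase, urinary retention and hematuria, could plausibly follow either operation, so attribution after RP would be uncertain.

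**The case against.** **This is an exploratory feasibility study.** It was sized for practical reasons and nobody would expect a powered safety test. That is fair, and the sample size is not the complaint. It is a reason for an estimate with an interval rather than a claim of proof.

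**Other safeguards exist.** The template rule and quarterly DSMC review protect patients during the study, and section 7.4 requires an attribution for each event. Section 10.7 already lists adverse events with any of the procedures for each patient. All of this stands, and it makes the requested split cheap. None of it says which events enter the 30% count or supports the word proved.

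**A stronger reading is tempting but not supported.** A reader might infer from section 7.1.2 that TMA could pass while clearly worse than the plan's own focal-therapy experience. That section reports "In our initial series of 100 consecutive men who underwent HIFU focal therapy for PCa, approximately 13% of the patient experienced adverse events", adds "No patient underwent additional intervention due to complications/adverse events", and says of TMA "As such, we expect lower chances of side effects". CDC grade III is defined as "Requiring surgical, endoscopic or radiological intervention", which suggests a grade III rate of 0 in 100; Fisher's exact test of a hypothetical 2/10 against 0/100 gives p = 0.0075. The documents do not carry that conclusion:

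- The HIFU series is cited as risk rationale, never as a benchmark or comparator.
- No CDC grading, follow-up window or separate grade IV–V count is given for it.
- It is described as HIFU alone, whereas the delayed-phase window here includes RP, so counted events need not be due to TMA.
- A ceiling described as clinically acceptable may properly sit above the rate that is expected, so the two figures do not contradict each other.

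The lack of a stated source for the 30% is likewise a missing detail, not an error.

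**Conclusion.** The concern holds as a fault in the decision rule and its wording. At n = 10, no passing result excludes a 30% severe-event rate at the two-sided 95% level, and a true rate of 30% passes with probability 0.65 or 0.38, depending on which stated limit applies. The two limits conflict at exactly 3 events. The count is not confined to TMA-related events, so RP complications can influence a verdict about TMA.

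The pass probabilities assume independent patients and one common rate across five escalating templates; the true rate may differ by template. The conclusion about 0/10 depends on the confidence level: a one-sided 95% limit (25.9%) would fall below 30%, but the plan specifies no level, and 1/10 fails even then. The last point assumes that the 30% rule uses the delayed-phase window to follow-up phase 3, since it states none of its own. Nothing here shows that 30% is the wrong limit, or that TMA compares badly with existing focal therapy.

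**What to change.** In section 10.7, with matching text in 7.7:

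1. **Conclusion.** Replace the statement that feasibility is proved with a statement that the observed CDC grade 3 or higher rate was, or was not, below the pre-set limit, given with its exact 95% interval. Add that a pass does not establish a true rate below 30%, or one similar to existing focal therapy. The HIFU series may be mentioned as context only.
2. **Counting.** Report CDC grade 3 or higher events separately from TMA to the start of RP anesthesia, and from then onward. State which count the limit applies to. The pre-RP biopsy shares the RP anesthesia, so it falls in the second period.
3. **Limit.** Reconcile the rate under 30% with the count of fewer than 4 in 10, so that the result at 3 events is fixed in advance. Which reading is right, and whether 30% is suitable, is for the sponsor; no limit is proposed here.

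The cost is a few sentences and one table. The calendar already schedules adverse event assessment on the TMA day, at Day 10, 1–5 days before RP, on the RP date and afterwards. No visits are added; only the onset of RP-day events relative to anesthesia needs recording. The downside is a less favourable safety conclusion, with wide intervals at n = 10.

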## **2.1 Primary Objectives**

To determine the feasibility of transperineal targeted microwave ablation of an MRI-identified index prostate cancer in patients undergoing radical prostatectomy.

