## **2.4 Primary Endpoints**

The ablated area on the radical prostatectomy specimen assessed by viability tissue staining (TTC).

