#### **10.3 Primary Objective Statistical Considerations**

To determine the feasibility of transperineal targeted microwave ablation of an MRI-identified index prostate tumor in patients undergoing radical prostatectomy, we will evaluate the viable tissue remaining after TMA using histologic examination of excised prostate specimen.

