#### **10.6 Sample Size and Patient Accrual**

Due to the nature of exploratory and feasibility study design, the sample size of 15 subjects was determined by practical considerations, including cost and feasibility (could not do many more during the funding period).

Through the immediate resection phase, 5 practical TMA templates and their ablation areas are evaluated. With following the delayed resection phase, the short-term safety and feasibility of TMA templates are evaluated.

The number of patients included may be extended considering the need to evaluate different treatment parameters (still according to manufacturer data).

---

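### The only rule that declares feasibility gives two answers at 3 severe events in 10, and its conclusion claims more than 10 men can show

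*Combined protocol and SAP*

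**What the plan says.** The safety bullet in section 10.7 (Data Analyses Plans) first states the standard: "we defined 30% as clinically acceptable severe adverse events", with severe meaning Clavien-Dindo grade 3 or higher. It then gives the decision rule: feasibility is concluded if these events "occur less than 30% (equivalent to less than 4 cases in 10 cases) for the delayed ablation phase, the feasibility of TMA is proved".

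Section 7.7 (Monitoring Rules for Safety) gives the same standard, "We set 30% as clinically acceptable severe adverse events", and explains it as "less than 4 in 10 delayed resection cases". It does not use the strict percentage.

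Feasibility is also the primary objective in section 2.1: "To determine the feasibility of transperineal targeted microwave ablation of an MRI-identified index prostate cancer". The primary endpoint in section 2.4 is histological: "The ablated area on the radical prostatectomy specimen assessed by viability tissue staining (TTC)". For the primary objective, section 10.3 says "we will evaluate the viable tissue remaining after TMA using histologic examination of excised prostate specimen" and sets no numerical criterion.

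The number of men is not fixed. Section 10.6 says "The number of patients included may be extended considering the need to evaluate different treatment parameters", and section 4.7 makes replacement of a removed patient optional.

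**The concern.** A pre-set decision rule should give one answer for every possible result. This one gives a pass and a fail at its own threshold. It is also the only sentence in the plan that turns data into a conclusion about feasibility: section 10.3 has no cut-off, and the rules in section 7.7 and the delayed-phase part of section 10.7 only pause enrolment or stop progression to the next template. If 3 of 10 men had a severe event, the reading could be chosen after the result was known.

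Two further points attach to the same sentence. It reports a pass as proof, although a pass in 10 men leaves rates well above 30% possible. And it draws a feasibility conclusion from a safety count alone, while the primary objective is analysed by histology.

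**Working it through.** **Inputs.** The limit is 30%, and the two forms of the rule come from section 10.7. The count is repeated in section 7.7. The denominator is the 10 delayed-resection men. The documents give no expected rate of grade 3 or higher events after TMA and no confidence level, so the true rates below are assumptions shown as a range.

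**Step 1: try to reproduce the stated equivalence (n = 10).**

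| Events | Rate | Below 30%? | At most 30%? | Fewer than 4? |
|---|---|---|---|---|
| 0 | 0% | pass | pass | pass |
| 1 | 10% | pass | pass | pass |
| 2 | 20% | pass | pass | pass |
| 3 | 30% | **fail** | pass | **pass** |
| 4 | 40% | fail | fail | fail |

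The equivalence is not reproduced. The count matches only if the percentage is read as 30% or less. The forms disagree at one result, 3 of 10.

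**Step 2: how much depends on the reading.** Let X be Binomial(10, p), that is, 10 independent men with a common rate p. The count form passes with probability P(X ≤ 3) and the percentage form with P(X ≤ 2). The difference is P(X = 3) = 120 × p³ × (1 − p)⁷. At p = 0.3 this is 120 × 0.027 × 0.08235 = 0.267.

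| True rate | Pass by count | Pass by percentage | Exactly 3 of 10 |
|---|---|---|---|
| 5% | 99.9% | 98.9% | 1.0% |
| 10% | 98.7% | 93.0% | 5.7% |
| 20% | 87.9% | 67.8% | 20.1% |
| 30% | 65.0% | 38.3% | 26.7% |
| 40% | 38.2% | 16.7% | 21.5% |
| 50% | 17.2% | 5.5% | 11.7% |

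**Step 3: what a pass shows.** The exact (Clopper-Pearson) upper limit for x events in 10 is the Beta(x + 1, 10 − x) quantile at 0.95 (one-sided 95%) or 0.975 (two-sided 95%). For x = 0 these are 1 − 0.05^(1/10) = 25.9% and 1 − 0.025^(1/10) = 30.8%.

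| Events | One-sided 95% upper limit | Two-sided 95% upper limit |
|---|---|---|
| 0 of 10 | 25.9% | 30.8% |
| 1 of 10 | 39.4% | 44.5% |
| 2 of 10 | 50.7% | 55.6% |
| 3 of 10 | 60.7% | 65.2% |

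Only 0 of 10 excludes a 30% rate, and only at one-sided 95%. At two-sided 95% it narrowly does not.

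**Step 4: other denominators.** A fixed count does not track 30% if the phase has more or fewer than 10 men. With 9 men, 3 events are 3/9 = 33%, which passes the count and fails the percentage. With 14 men, chosen only for illustration, 4 events are 4/14 = 29%, which fails the count and passes the percentage.

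**The case against.** - **The intended limit can largely be inferred.** Sections 7.7 and 10.7 both call 30% itself acceptable and both give the same count. Only the strict inequality in section 10.7 does not fit, so a drafting slip is likely. This stands as an explanation, but the strict form sits in the sentence that declares the conclusion, and no text says the count takes precedence.
- **The disputed result may be unlikely.** This is fair at low rates: 1.0% at a true rate of 5% and 5.7% at 10%. The documents give no expected rate, so the whole range has to be shown.
- **The stop rule is left out of the pass probabilities.** Severe TMA-related events in both men on one template stop progression. Suppose every event counts for both rules and a stop on templates 1 to 4 means that no feasibility conclusion is reached. At a 30% rate the pass probabilities become 56% by the count and 36% by the percentage, with 20% on exactly 3 of 10. At 40% they become 31% and 16%. The gap narrows but remains, and an early stop is itself a way to end with fewer than 10 men. A common rate across five escalating templates is also a simplification.
- **Safety is a legitimate part of feasibility.** Section 1.4 lists efficacy, precision and safety, and section 10.6 assigns short-term safety and feasibility to the delayed phase. This stands. The criticism is only that a safety count cannot be the whole of feasibility when the Study Summary pairs the primary objective with ablated area and section 10.3 analyses it by remaining viable tissue.
- **An exploratory criterion on an observed count need not exclude 30%.** Agreed. That is a reason not to call the result proof.
- **Readers would see the 3 of 10 anyway.** Adverse events are listed by patient, so the data would not be hidden. The label attached to them would still be open to choice.

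**Conclusion.** The concern holds. With 10 men the percentage passes 0 to 2 events and the count passes 0 to 3, so the plan's only feasibility rule contradicts itself at 3 of 10. This part is plain arithmetic and needs no assumption beyond the planned denominator. The choice of reading moves the chance of a pass by about 6 percentage points at a true rate of 10%, 20 at 20%, 27 at 30% and 21 at 40%. These figures assume 10 independent men with a common rate and no early stop.

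The claim of proof is unsupported for 1, 2 or 3 events at either confidence level considered, and for 0 events it depends on a level the plan does not state. The histological analysis of the primary endpoint and the pause and stop rules are not affected. The sentence must be corrected before delayed-phase results are known, because a later choice of limit could follow the data.

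**What to change.** 1. Reconcile the percentage and the count in section 10.7 with each other and with section 7.7. The sponsor chooses the limit. If it is 30% or less, at most 3 of 10, only section 10.7 changes. If it is below 30%, at most 2 of 10, the count changes in both sections.
2. State how the rule applies if the delayed phase does not have exactly 10 men, whether through early stopping, removal without replacement, or extension.
3. Replace the claim that feasibility is proved with a statement that the pre-set short-term safety criterion is met.
4. Report the number of men with a severe event with an exact (Clopper-Pearson) confidence interval, its level and sidedness fixed in advance.

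The cost is rewording in one or two sections and one interval. No patients or procedures are added. The conclusion a pass supports becomes more modest.
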